1.2 Ga-PSMA PET in Newly Diagnosed and Biochemically Recurrent Prostate Cancer

Ga-PSMA PET is one of several novel molecular imaging modalities that have recently emerged in the field of prostate cancer.⁶ Using radiolabeled small molecules targeted at PSMA on the surface of prostate cancer cells, Ga-PSMA PET demonstrates excellent tumor-to-background ratio with little physiological uptake in normal tissue. It is not limited by morphologic size criteria, and unlike bone scintigraphy can directly visualize bony metastasis.⁶ Ga-PSMA PET imaging has had a significant impact on the management of early state prostate cancer. In a recently published multicenter randomized trial of 302 men with high-risk, clinically localized disease, Ga-PSMA PET was more accurate than conventional imaging with CT and bone scanning for identifying pelvic nodal or distant metastases.⁸ Other studies have also shown increased sensitivity and specificity over conventional imaging for the localization of recurrent disease in patients with rising PSA after definitive therapy.^{9,10} Although its impact on patient outcomes remains to be determined, Ga-PSMA PET is quickly emerging as an alternative to conventional imaging for the staging of men with early prostate cancer.

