2.3 Secondary Objective(s) and Endpoint(s)

Secondary Objective	Endpoint(s)	Time Frame
1. To determine whether the percent change from baseline in $SUV_{max-ave}$ on PSMA PET is associated with time-to-event endpoints including PSA progression-free survival by Prostate Cancer Clinical Trials Working Group 3 (PCWG3) ²⁶ criteria and overall survival.	Association between percent change from baseline in $SUV_{max-ave}$ on PSMA PET with time-to-event endpoints including PSA progression-free survival by PCWG3 criteria and overall survival.	Baseline to time of progression Baseline to time of death
2. To determine whether the percent change from baseline in SUV_{max} on PSMA PET is associated with objective response by Response Evaluation Criteria in Solid Tumors (RECIST) version 1.1 ²⁷ on a per-lesion basis among measurable soft tissue lesions present at baseline	Association between percent change from baseline in SUV_{max} on PSMA PET with objective response by RECIST 1.1 on a per-lesion basis among measurable soft tissue lesions present at baseline.	Baseline to time of objective response

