7.1 Imaging Analysis

A trained nuclear medicine physician will evaluate the reconstructed PET, CT or MRI, and fused PET/CT or PET/MR images using a PET volume computer-assisted reading software package. A positive lesion on PET will be defined as a focus of activity with higher SUV compared with mediastinal blood pool that is not attributable to other etiologies of tracer distribution (e.g. inflammation, excretion). A volume of interest (VOI) will be semi-automatically placed around each lesion, and the calculated maximum standard uptake value (SUV_{max}) will be recorded for each lesion, including lesions that are detected on standard scans but are not positive on PET. Adjusted SUV_{max} data will then be averaged the primary tumor and 5 largest lesions in each of three metastatic site (nodal, visceral, and osseous) within a given patient, up to a maximum of 16 lesions per patient ($SUV_{max-avg}$). Irradiated lesions will be excluded from this analysis.

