7.4.3 Secondary Analysis (or Analysis of Secondary Endpoints)

The study cohort will be dichotomized by the median with respect to percent change from baseline in $SUV_{max,ave}$ on PSMA PET. The time-to-event variables including PSA progression-free defined by PCWG3, and overall survival will be compared between dichotomized subgroups using the log-rank test. Kaplan-Meier product limit method will be used to estimate median survival in each subgroup.

Amongst the subset of measurable soft tissue lesions by RECIST 1.1 criteria, on a per-lesion basis, the mean percent change from baseline in SUV_{max} on PSMA PET will be compared between responding lesions by RECIST 1.1 criteria vs. those without response, using Mann-Whitney test.

PSMA negative lesions will be defined as those with SUV values below the mediastinal blood pool. Low positive lesions will be defined as those with SUV_{max} values above the blood pool, but below background liver uptake. Intermediate positive lesions are those defined by SUV_{max} values above background liver, but below parotid gland uptake. High positive lesions are those with SUV_{max} values above that of parotid gland. The histologic, genomic and transcriptional features of each subgroup of PSMA lesion category that has matching tumor tissue will be descriptively reported with particular emphasis on the low and negative PSMA lesions that have paired tumor tissue available.

The median and range for inter-tumoral SUV_{max} across metastatic lesions within individual patients will be descriptively reported, to assess for heterogeneity of PSMA uptake. The cohort will be dichotomized above and below median range of SUV_{max} values to define low and high heterogeneity subgroups. Overall survival from date of onset of mCRPC will be compared between high vs. low heterogeneity subgroups.

Analysis of the correlation between SUV_{max} PSMA and FDG PET will be performed on a per-lesion basis amongst the subset of patients who have paired evaluable imaging using Pearson r correlation coefficient.

Patterns of PSMA expression at the time of progression by PCWG3 criteria will be descriptively characterized.

Comparison of mean percent change from baseline in $SUV_{max,ave}$ in PSA50 responders vs. non-responders will be performed in pre-specified subgroups based on modality of systemic

treatment, including AR targeted therapy, PSMA-directed radioligand therapy, cytotoxic chemotherapy, and immunotherapy.

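### Secondary objective 2 groups lesions by size response and compares their SUVmax change with no size check, so an association may partly or wholly reflect lesion size rather than PSMA uptake

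*Combined protocol and SAP*

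**What the plan says.** Section 2.3 sets secondary objective 2 as an association between percent change in SUVmax and RECIST 1.1 objective response, "on a per-lesion basis among measurable soft tissue lesions present at baseline". Section 7.4.3 turns this into a two-group comparison by Mann-Whitney test: SUVmax change "will be compared between responding lesions by RECIST 1.1 criteria vs. those without response".

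Section 7.1 describes the measurement. "A volume of interest (VOI) will be semi-automatically placed around each lesion", and the maximum SUV in it "will be recorded for each lesion". The next sentence says that *Adjusted* SUVmax data are averaged within the patient. The adjustment is not explained, and the per-lesion paragraph of Section 7.4.3 does not use the word.

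No section names a partial-volume correction, a size covariate, a size stratum or a minimum diameter beyond measurability. Section 5.3.6 asks for the same modality (PET/CT or PET/MR) at both scans. That does not remove a loss that depends on lesion size on one and the same type of scanner.

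**The concern.** The grouping variable is change in lesion size, and the outcome is the peak PET reading of the same lesion. Because PET has finite resolution, the peak of a small object depends on its size as well as its uptake. The two variables are therefore mechanically linked, and the link runs toward a larger SUVmax fall in responding lesions.

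What is at stake is interpretation. The hypothesis in Section 2.1 concerns decline in uptake. A positive result would naturally be read as PSMA uptake falling where lesions respond. As planned, that reading cannot be separated from smaller objects giving lower readings.

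**Working it through.** **The plan's own figure.** The documents give no power, lesion count or lesion size for secondary objective 2. The nearest figure is the 89% power of the primary test in Section 7.2.1 (40 vs 60 patients, difference 20 points, SD 30, two-sided 0.05). With the Mann-Whitney efficiency 3/π: (20/30) × √(40 × 60/100 × 3/π) − 1.96 = 0.667 × 4.787 − 1.96 = 1.23, which gives 89.1%. It reproduces and is not in dispute. It is used here only for scale.

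**Size-only change in SUVmax.** Assumptions, none of them in the documents: spherical lesion, Gaussian resolution of 5 to 7 mm FWHM, lesion-to-background 10:1, true uptake unchanged, response taken as a diameter decrease of at least 30%.

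- σ = FWHM/2.355 and x = radius/σ.
- Recovery RC = erf(x/√2) − √(2/π) · x · exp(−x²/2).
- Measured peak = 1 + 9 · RC (background 1, lesion 10).

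Example: 15 to 10.5 mm at 6 mm FWHM. σ = 2.548. Baseline x = 7.5/2.548 = 2.944, RC = 0.966, peak 9.69. Follow-up x = 5.25/2.548 = 2.061, RC = 0.764, peak 7.88. The change is about −19%.

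| Diameter change | 5 mm | 6 mm | 7 mm |
|---|---|---|---|
| 15 to 10.5 mm (−30%) | −9% | −19% | −27% |
| 20 to 14 mm (−30%) | −1% | −5% | −11% |
| 30 to 21 mm (−30%) | 0 | 0 | about −0.5% |
| 20 to 10 mm (−50%) | −12% | −25% | −37% |
| 25 to 12.5 mm (−50%) | −3% | −10% | −20% |

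The effect is large in small lesions and near zero in large ones that shrink moderately. At 25 mm a 30% decrease gives −0.1, −0.7 and −3%, but a 50% decrease can still matter.

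**How often the planned test would reject.** Simulated: 40 independent lesions, 35% responding, log-normal baseline diameters limited to 10 to 60 mm, responders shrinking about 45%, others within ±15%, and true uptake change unrelated to response. The ranges cover 5 to 7 mm resolution.

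| Median baseline diameter | Log SD of uptake change 0.30 | Log SD 0.60 |
|---|---|---|
| 15 mm | about 62–98% | about 29–72% |
| 20 mm | about 28–82% | about 10–44% |
| 25 mm | about 16–50% | about 8–22% |

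These rates move by several points with the spread chosen for diameters and shrinkage. Tested on true uptake itself, the rejection rate is 4–6%, as it should be. The 0.30 is close to the 30% SD in Section 7.2.1, but that SD belongs to an average over up to 16 lesions. Single lesions are probably more variable, hence the second column. Clustering of lesions within patients is a separate matter and is not modelled.

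**The case against.** **The objective claims only an association.** Section 2.3 asks whether SUVmax change is associated with response. A lower measured SUVmax in shrinking lesions is a true association. This stands. A reader might infer that a positive result would be false or the test invalid, and the documents do not support that. The weakness lies in reading the result as a change in uptake.

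**SUVmax may not be uncorrected.** Section 7.1 records SUVmax per lesion and then averages *Adjusted* values, so some adjustment may be made lesion by lesion. This stands too. If the word means a partial-volume correction that also applies in Section 7.4.3, the point is largely met. The text does not say.

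**The rationale does not promise independence from size.** Section 1.2 says of PSMA PET, "It is not limited by morphologic size criteria". A reader might take that as a claim about SUVmax. In context it contrasts PET with conventional imaging in newly diagnosed and recurrent disease.

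**The rejection rates rest on inputs outside the documents.** True. Doubling the log SD lowers them considerably, and with mostly large lesions the problem nearly disappears.

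**Stronger remedies fail.** Recovery correction looks perfect in simulation only because the data are corrected with the model that generated them. Real lesions that vanish have no diameter to correct with, very small ones have their noise multiplied, and Section 5.3.1 allows baseline CT or MRI up to 12 weeks from baseline PET. Requiring significance in lesions of at least 25 mm would also be unsound: a true 20% fall in uptake would be detected there only about 1–36% of the time in simulation.

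None of this removes the need for a size-stratified report. It limits what that report can be asked to prove.

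**Conclusion.** The concern holds as a limit on interpretation of secondary objective 2. On the stated assumptions, shrinkage alone can produce an SUVmax fall that, in lesions of about 15 mm, approaches or exceeds the 20-point difference used to size the primary endpoint. In lesions of about 30 mm with moderate shrinkage it produces almost none. Where this trial falls between those ends cannot be settled from the documents.

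A reader might extend the point to the primary analysis. That comparison is split by PSA50, not by lesion size, so this argument does not bear on it directly.

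**What to change.** Keep the planned Mann-Whitney comparison as it is, and make three additions before results are seen.

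1. In Section 7.4.3, add a pre-specified supportive analysis: the same comparison reported as an estimated difference in percent change with its confidence interval, by baseline-diameter stratum (for example, below 25 mm and at least 25 mm).
2. In the same section, state that a difference confined to small lesions will not be read as evidence of a fall in PSMA uptake.
3. In Section 7.1, say what *Adjusted* means, whether it includes a partial-volume correction, and whether it applies to the per-lesion analysis.

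Recovery-corrected SUVmax may be added, as exploratory only.

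The cost is SAP wording and a short analysis using diameters that the RECIST assessment already needs. No scan, visit or patient is added. The strata will be small and the intervals wide, so the large-lesion stratum should be read by its estimate and interval, with no significance requirement. A 25 mm cut reduces the size effect but does not abolish it when lesions shrink by half, and the report should say so.

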1.4 Rationale for Inclusion of Optional Paired Tumor Biopsy and FDG-PET

Whereas PSMA is uniformly expressed in the early prostate cancer, variable levels of PSMA expression have been reported in patients with castration-resistant disease.²¹ PSMA expression is inversely related to neuroendocrine biomarker genes,²¹ and treatment-emergent small-cell neuroendocrine prostate cancer (SCNC) may present as a low-uptake lesion on PSMA-based imaging.²² Additionally, up to 25% of patients screened for enrollment in PSMA-targeted radioligand therapy fail to meet inclusion criteria due to low- or heterogeneous-PSMA expression.^{11,12,23} “Discordant” metastases on serial Ga-PSMA- and FDG-PET imaging, with low PSMA and high Fluorodeoxyglucose (FDG) uptake, have also been described. Limited existing data on this subset of patients suggests a particularly aggressive cancer phenotype,²³ however the histologic and genomic features of this disease entity have yet to be defined. Furthermore, heterogeneous treatment effect and/or prior localized therapy may also contribute to intra-patient variations in PSMA expression. To address this and to better differentiate treatment-related PSMA suppression from discordant disease, we will offer an optional FDG-PET scan to patients with low- or heterogeneous PSMA uptake.²⁴ Additionally, we will offer optional paired tumor biopsies in selected patients with low PSMA expression, or heterogeneous PSMA uptake on Ga-PSMA PET imaging. As the use of Ga-PSMA PET imaging in mCRPC increases, there is an urgent need to better characterize these different patterns of PSMA expression. By quantifying variations in PSMA expression levels in patients with mCRPC, Ga-PSMA PET may offer non-invasive molecular insight into the underlying biology of advanced prostate cancer.

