2.4 Exploratory (Correlative) Objectives

Exploratory Objective
1. To descriptively characterize the histologic, transcriptional, and genomic features of PSMA low/negative lesions among patients who undergo paired optional metastatic tumor biopsy.
2. To descriptively characterize the relationship between $SUV_{max-ave}$ on baseline Ga-PSMA PET with optional baseline FDG-PET.
3. To determine whether heterogeneity of PSMA expression on baseline Ga-PSMA PET is associated with overall survival.
4. To descriptively characterize the patterns of PSMA expression at the time of disease progression among patients who undergo optional PSMA PET.
5. To determine whether the percent change from baseline in PSMA PET is associated with PSA50 response among subgroups of patients defined by treatment modality received, including AR targeting treatment, PSMA-targeting radioligand therapy, cytotoxic chemotherapy, and immunotherapy.

3 Study Design

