7.4.2 Primary Analysis (or Analysis of Primary Endpoints)

The mean ($SUV_{max,ave}$), median, and range of SUV_{max} across the primary tumor and the 5 largest lesions in each of three metastatic sites (nodal, visceral and osseous; for a maximum of 16 lesions per patient) will be descriptively reported. The study cohort will be divided into subgroups based on whether or not patient experienced a $\geq 50\%$ decline from baseline in serum PSA (PSA50 responder) or not (PSA50 non-responder). The mean percent change from baseline in $SUV_{max,ave}$ on PSMA PET between PSA50 responders vs. non-responders will be compared using the Mann-Whitney test.

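### The per-lesion Mann-Whitney test for secondary objective 2 treats lesions from one patient as independent, so its p-value is too small if SUVmax change and RECIST response both cluster within patient

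*Combined protocol and SAP*

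**What the plan says.** Section 2.3 frames secondary objective 2 as an association between percent change in SUVmax and RECIST 1.1 response "on a per-lesion basis among measurable soft tissue lesions present at baseline". Section 7.4.3 keeps the lesion as the unit ("Amongst the subset of measurable soft tissue lesions by RECIST 1.1 criteria, on a per-lesion basis, the mean percent change from baseline" in SUVmax) and compares "responding lesions by RECIST 1.1 criteria vs. those without response, using Mann-Whitney test".

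Section 7.1 states that SUVmax "will be recorded for each lesion, including lesions that are detected on standard scans but are not positive on PET". Its limit of 5 lesions per metastatic site, 16 in all with the primary tumor, defines the SUVmax-ave average only. No section limits or states how many measurable lesions a patient may contribute to the RECIST comparison.

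Sections 7.1 to 7.4 contain no mixed model, GEE, clustered rank test, patient-level bootstrap, patient-level summary or one-lesion-per-patient rule for this analysis. The waiver of multiplicity adjustment at the end of Section 7.4.3 is a separate matter.

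**The concern.** The Mann-Whitney null variance is derived for independent observations. Lesions in one patient share the same systemic therapy and the same scan dates. Patients differ in modality, and Section 5.3.6 sets the follow-up PET at 20 weeks (+/- 4) for AR-targeted therapy and at 12 weeks (+/- 4) for the other listed modalities. Between-patient variation in both SUVmax change and size response is therefore plausible, and such variation is the same thing as within-patient correlation.

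If both variables cluster, the test rejects a true null more often than its nominal level. Separately, and whether or not there is clustering, patients with many lesions weigh more than patients with few.

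The plan answers secondary objective 2 with this test alone. The primary analysis averages lesions within patient before testing and so avoids the problem; this analysis does not.

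**Working it through.** **1. The plan's own figure.** The only power statement is for the primary test (Section 7.2.1): 40 vs 60 patients, effect size 0.67 (20/30 = 0.667), two-sided 0.05, 89% power. A noncentral t calculation with sample sizes multiplied by the Mann-Whitney efficiency 3/π = 0.955 (38.2 and 57.3) gives 88.8%. A simulated Mann-Whitney test (20,000 runs) gives 88.9%. The figure reproduces. It is at patient level, so clustering of lesions does not touch it.

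**2. Inputs for secondary objective 2.** From the documents: the lesion as unit, the ordinary Mann-Whitney test, no cluster term. Assumed, because the documents give none: a 5% two-sided level (stated only for the primary), the number of patients with measurable lesions, lesions per patient *m*, the lesion response rate, and the within-patient correlations ρx (SUVmax change) and ρr (response).

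**3. Analytic check, equal *m*.** The variance of the rank-sum statistic is inflated by about

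Deff = 1 + (m − 1)·ρx·ρr, and the true error is 2[1 − Φ(1.96/√Deff)].

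Example: m = 3, ρx = ρr = 0.5. Deff = 1 + 2 × 0.25 = 1.50; 1.96/√1.50 = 1.60; error = 11.0%.

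| m | ρ = 0.2: Deff, error | ρ = 0.3: Deff, error | ρ = 0.5: Deff, error |
|---|---|---|---|
| 2 | 1.04, 5.5% | 1.09, 6.0% | 1.25, 8.0% |
| 3 | 1.08, 5.9% | 1.18, 7.1% | 1.50, 11.0% |
| 5 | 1.16, 6.9% | 1.36, 9.3% | 2.00, 16.6% |
| 10 | 1.36, 9.3% | 1.81, 14.5% | 3.25, 27.7% |

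The product ρx·ρr shows why both variables must cluster: if either is 0, Deff = 1. Null simulations (3,000 runs per setting, 40% of lesions responding, 30 to 100 patients) agree with this formula within about 1.5 points.

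**4. Simulation with varying lesion counts.** 10,000 null replicates per cell, 50 patients, 35% of lesions responding, lesion counts uniform over the range, normal patient effects, response correlation on the latent scale. Monte Carlo error is about 1.96·√(0.05 × 0.95/10,000) = 0.4 points near 5%.

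| Lesions per patient | ρ = 0.3 | ρ = 0.5 | ρ = 0.7 |
|---|---|---|---|
| 1–3 | 5.6% | 7.6% | 10.3% |
| 1–5 | 7.1% | 9.8% | 14.7% |
| 1–10 | 8.8% | 15.7% | 25.8% |

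Controls: 4.8–5.2% with one lesion per patient, and 4.7–5.1% when either correlation is 0. The number of patients hardly matters: 1–5 lesions gives 6.2/9.7/14.8% with 30 patients and 6.9/10.5/15.1% with 70. These values tend to lie below those in step 3 because a given latent correlation corresponds to a smaller correlation of the binary response.

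**5. Weak correlation.** With latent correlations of 0.1–0.2 in both variables and 30–70 patients (3,000 replicates, Monte Carlo error about 0.8 points), the error is 4.3–5.9% with 1–3 lesions, 4.5–5.3% with 1–5 and 5.3–7.3% with 1–10.

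**6. Remedy.** A regression of ranks on response with patient-clustered variance gives 5.3–6.5% on the clustered data of step 4. A further run of cluster-robust rank and mean (GEE-type) tests gives 5–7% with 50 patients and up to 7.7% with 30.

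**The case against.** The strongest reply is that the harm is conditional and may be small. The documents give no correlation, no lesion count and no number of patients with measurable disease; eligibility requires one PSMA-avid metastatic lesion, not a measurable one. Steps 3 and 5 show little inflation when correlation is weak and lesions are few. The 10-lesion case borrows a limit (5 nodal + 5 visceral) that does not govern this analysis. Section 1.4 also notes that heterogeneous treatment effect and prior local therapy "may also contribute to intra-patient variations in PSMA expression", which argues against strong clustering, although it concerns uptake rather than its percent change. All of this stands. It limits the size that can be claimed, but it does not make the independence assumption safe, and the plan cannot know beforehand that clustering is weak.

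Two points about the remedy also stand. A cluster-robust variance corrects the error rate but leaves every lesion with equal weight, so unequal patient weights remain unless the method changes them. A mixed or GEE model of percent change compares means rather than ranks.

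Finally, this is one secondary analysis in a phase 2 imaging study, with no level, power or decision rule of its own. That lowers the priority but does not remove the point, because a stated objective rests on this test alone.

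**Conclusion.** The concern holds as a conditional statement: the specified test ignores the patient, and its type I error exceeds 5% when SUVmax change and lesion response both cluster. Under moderate assumptions (1–5 lesions per patient, latent correlation 0.3–0.5, 50 patients) the error is about 7–10%. With equal lesion counts of 2–5 and the same correlations on the observed scale it is about 6–17%. It is near nominal for weak correlation with few lesions, and at nominal if only one variable clusters. All correlations, lesion counts and response rates are assumptions. N = 100 and the 89% power of the primary analysis are not affected. This should be fixed, but it does not threaten the trial's main conclusion.

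**What to change.** In Section 7.4.3, replace the ordinary Mann-Whitney test for this objective with one of:

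- a rank-sum test for clustered data, in a version that allows responding and non-responding lesions within the same patient;
- a GEE or mixed model of lesion SUVmax change on lesion response with patient as cluster, accepting that it compares means.

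State the significance level and whether lesions or patients receive equal weight. Report the number of patients and the distribution of lesions per patient. If few patients have measurable lesions, note that cluster-robust tests can still run slightly above nominal.

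A lesser companion sits in the same section. The PSMA–FDG correlation "will be performed on a per-lesion basis amongst the subset of patients who have paired evaluable imaging using Pearson r correlation coefficient", while exploratory objective 2 in Section 2.4 names SUVmax-ave "on baseline Ga-PSMA PET with optional baseline FDG-PET". The two should be reconciled. The lesion-level analysis is worth keeping, since Section 1.4 motivates FDG PET by discordant lesions. The coefficient is descriptive and no p-value or interval is planned; if one is reported, it should come from a bootstrap that resamples patients.

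The cost is revised wording and a few lines of code, with no new data or patients. Because Section 7 is part of the protocol, Section 8.4 requires an amendment signed by the principal investigator and approved by the PRC and IRB; it should be made before database lock. The statistical price is a less favourable p-value where clustering is present.

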1.5 Overall Study Rationale

⁶⁸Ga-PSMA-PET has been shown to have significant utility and clinical impact in the detection of prostate cancer in newly diagnosed and biochemically recurrent patients. Preliminary retrospective evidence suggests that in patients with metastatic castration resistant prostate cancer, decline from baseline in PSMA PET upon application of systemic therapies in mCRPC may be associated with subsequent response, however this link has not been definitively established. A subset of patients with mCRPC may also present with low or heterogeneous PSMA expression, which may be associated with a poor prognosis. We aim to prospectively investigate the association between response on PSMA PET with subsequent treatment outcomes. We also hope to describe the clinical histologic, genomic features of patients with low or heterogeneous PSMA expression.

2 Study Objectives and Hypotheses

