3.3.1 Inclusion Criteria

1. Sub-cohort A1: Patients must have baseline evaluations performed within 12 weeks prior to the start of systemic therapy. (*Note: Patients in sub-cohort A1 who initiate systemic therapy during the screening period/prior to study enrollment may be re-consented to transition to sub-cohort A2.*)
2. Sub-cohort A2: Patients must meet **all** the following requirements:

- Have had a baseline pre-treatment 68Ga-PSMA-11 PET scan and PSA measurement performed within 12 weeks prior to the start of current systemic therapy.
- Able to have an on-treatment 68Ga-PSMA-11 PET and a PSA measurement within 16 weeks (+/- 8 weeks) after the start of current systemic therapy.

Note: The screening period for sub-cohort A2 is within 24 weeks after the patient started their current systemic therapy.

3. Patients must have progressive castration resistant prostate cancer, according to PCWG3 criteria.
4. Patients must have planned initiation of systemic treatment (sub-cohort A1), or ongoing systemic treatment (sub-cohort A2) for castration resistant prostate cancer within 12 weeks of baseline Ga-PSMA PET.
5. Patients must have at least one metastatic lesion with PSMA uptake at or above the blood pool on their baseline PSMA PET scan.
6. The patient must be able and willing to comply with study procedures and provide signed and dated informed consent.
7. Patient must have an Eastern Cooperative Oncology Group (ECOG) Performance Status of 0 or 1.
8. Patient must be Aged 18 years or older at the time of study entry
9. Patients who undergo optional metastatic tumor biopsy following completion of baseline Ga-PSMA PET (sub-cohort A1) must additionally meet all of the following criteria:
 - Presence of one or more metastases by standard radiographic scans that is safely accessible to tumor biopsy in the judgment of treating clinician and/or Interventional Radiology.
 - No history of radiation therapy to the target metastatic lesion selected for tumor biopsy
 - No contra-indication to biopsy including uncontrolled bleeding diathesis.
 - Platelets >75,000/ μ L and PT or INR and a PTT < 1.5 times the institutional ULN within 14 days prior to biopsy

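### The SUVmax range that defines heterogeneity rises with lesion count, so the survival comparison for exploratory objective 3 is confounded with disease burden and possibly with PSMA level

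*Combined protocol and SAP*

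**What the plan says.** Exploratory objective 3 in section 2.4 is inferential, not descriptive: "To determine whether heterogeneity of PSMA expression on baseline Ga-PSMA PET is associated with overall survival". Section 7.4.3 gives the method in three sentences. The measure: "The median and range for inter-tumoral SUV_{max} across metastatic lesions within individual patients will be descriptively reported, to assess for heterogeneity of PSMA uptake". The grouping: "The cohort will be dichotomized above and below median range of SUV_{max} values to define low and high heterogeneity subgroups". The comparison: "Overall survival from date of onset of mCRPC will be compared between high vs. low heterogeneity subgroups".

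The range is on the absolute SUV scale. Section 7.4.3 states no minimum number of lesions, no adjustment for lesion count or mean uptake, and no test for this comparison.

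Two passages elsewhere bear on how many lesions enter the range. Section 3.3.1 requires a single qualifying lesion: "Patients must have at least one metastatic lesion with PSMA uptake at or above the blood pool on their baseline PSMA PET scan". Section 7.1 caps the averaged SUVmax at "up to a maximum of 16 lesions per patient", made up of the primary tumour and five lesions in each of three metastatic sites. If that cap also governs the range, which 7.4.3 does not say, a patient can contribute at most 3 × 5 = 15 metastatic lesions.

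**The concern.** A range is a maximum minus a minimum. Each further lesion can widen it and none can narrow it. Two patients whose lesions vary to the same degree will therefore tend to fall on opposite sides of the median split if one has three lesions and the other twelve. If spread also grows with uptake, the same happens between a patient with low uptake and one with high uptake.

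Lesion count reflects burden, and burden or PSMA level may well carry prognostic information of their own. A survival difference between the two groups could then come from either and be reported as an effect of heterogeneity. A real effect of heterogeneity could equally be diluted, because patients are sorted largely on something else.

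**Working it through.** The plan gives no figure for this analysis, so there is nothing of its own to reproduce; the 89% power in 7.2.1 belongs to the primary comparison. The documents also give no distribution of lesion counts or SUVmax. All distributions below are assumptions, and results are shown over a range of them.

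**1. Expected range against lesion count.** For n independent normal values with standard deviation σ, E(range) = σ ∫ [1 − Φ(z)^n − (1 − Φ(z))^n] dz. For n = 2 this is 2σ/√π = 1.13σ.

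| Lesions | 1 | 2 | 3 | 5 | 10 | 15 | 16 |
|---|---|---|---|---|---|---|---|
| E(range)/σ | 0 | 1.13 | 1.69 | 2.33 | 3.08 | 3.47 | 3.53 |

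At equal variability the ratio between 16 and 2 lesions is 3.53/1.13 = 3.1. For lognormal values with a coefficient of variation (CV) of 0.5, the expected range for 2, 3, 5, 10 and 15 lesions is 0.52, 0.79, 1.09, 1.47 and 1.70 times the patient's mean.

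**2. Range against uptake.** At a fixed CV, multiplying all of a patient's values by k multiplies the range by k, so doubling uptake doubles the range. If the absolute SD is the same at every level, this link disappears. The documents do not say which is closer to the truth.

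**3. What the median split does.** Simulation of 200,000 patients, median patient SUV 12, SD of log patient level 0.5, and the same true variability in everyone.

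| Assumption | Mean lesion count, high group | Low group |
|---|---|---|
| CV 50%, 1–16 lesions equally likely | 10.3 | 6.7 |
| Constant absolute SD, 1–16 equally likely | 11.1 | 6.0 |
| CV 50%, 8–15 lesions | 11.7 | 11.3 |

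In the first row the share classed as high is 0% with one lesion, 19% with 2–3, 41% with 4–6, 57% with 7–10 and 69% with 11–16. In the second row it is 9% with 2–3 and 79% with 11–16. By uptake, 12% of the lowest quartile and 81% of the highest are classed as high in the first row, against 50% and 50% in the second. The 12% and 81% describe one scenario and are not a bound: when counts vary less, uptake takes a larger share of the ranking.

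**4. What this does to the survival comparison.** Simulated cohorts of 100; lognormal SUVmax; CV centred on 0.5 and varying between patients (SD of log CV 0.3 or 0.6); 1–15 or 2–15 lesions; median survival 24 months; about 56 deaths; log-rank test at two-sided 5%; 1,000 to 1,500 runs per case. The Monte Carlo standard error near 5% with 1,500 runs is √(0.05 × 0.95/1500) = 0.6 points.

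| What truly affects survival | Rejection with the range split |
|---|---|
| Nothing | about 5–6% |
| Lesion count only (HR 1.5 per SD) | 13–22% |
| Uptake level only (HR 0.67–0.7 per SD) | 23–31% |
| Count and level, same direction | 51–63% |
| Heterogeneity only (HR 1.5 per SD) | 8–20% |

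In one scenario where count and level acted in opposite directions they cancelled (4.6%), so the bias has no fixed sign. The rank correlation of the range with the patient's true CV was 0.25–0.49; with mean uptake it was 0.55–0.70.

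**5. An alternative measure.** With the SD of log SUVmax in patients with at least two lesions, rejection when only count or only level mattered fell to 5–6%, and power for the heterogeneity effect rose to 27–49%. Its correlation with true CV was 0.55–0.80. It is not wholly free of count: in the equal-CV simulation the share above the median still rose from 0.37 with 2–3 lesions to 0.55 with 11–16.

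**The case against.** Several things can be said for the plan, and some of them stand.

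- A reader might infer that the analysis tests burden and PSMA level instead of heterogeneity, or cannot address objective 3 at all. That goes too far. A simulation in which every patient has the same variability leaves the range nothing real to detect. Once variability differs between patients, the range does track it (0.25–0.49), and the test holds its size when neither count nor level is prognostic.
- The uptake dependence is conditional on spread scaling with level, and the count imbalance nearly vanishes when most patients have many lesions. Both limits stand.
- A reader might infer from 3.3.1 that a patient entering on one lesion has range 0. The criterion concerns one PSMA-positive metastatic lesion, and 7.1 records SUVmax for others too, "including lesions that are detected on standard scans but are not positive on PET". Only a patient with one measured metastatic lesion is sure to have range 0.
- Section 1.5 says "A subset of patients with mCRPC may also present with low or heterogeneous PSMA expression, which may be associated with a poor prognosis". A reader might infer that placing uniformly low-uptake patients in the low-heterogeneity group contradicts this. It does not: low and heterogeneous are two separate states, objective 3 concerns the second, and such patients have little relative spread under any sensible measure. This is not a defect of the range.
- Absolute spread could be deliberate, since 7.4.3 grades lesions against blood pool, liver and parotid. That is a fair reason to keep the range as a reported quantity. It does not answer the dependence on lesion count.
- Section 7.4.3 reports each patient's median beside the range. That gives context on level but adjusts for nothing.

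**Conclusion.** The point holds as confounding. As written, the high and low groups will tend to differ in lesion count whenever counts vary materially between patients, and in uptake level if spread scales with level. The count dependence is mathematical and does not rest on the lognormal assumption. Its size is uncertain: a difference in mean count of about 4 to 5 lesions if 1 to 16 are equally likely (10.3 − 6.7 = 3.6; 11.1 − 6.0 = 5.1), and about 0.4 if counts lie between 8 and 15 (11.7 − 11.3). The uptake effect runs from none to strong, depending on the assumed spread. Neither a positive nor a null result could be read as evidence about heterogeneity without further analysis.

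The severity is minor. One of five exploratory objectives is affected, no power is claimed for it, and the primary endpoint and sample size are untouched.

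**What to change.** In 7.4.3:

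1. For patients with at least two baseline metastatic lesions, define heterogeneity as the SD of log SUVmax, or SD/mean.
2. Relate it to overall survival in a Cox model that also includes lesion count and the patient's mean SUVmax. Count stays in the model because the SD of log SUVmax retains some dependence on it.
3. Report one-lesion patients separately.
4. Keep the range, and if wanted its median split, as a descriptive or sensitivity measure.
5. State whether the lesion cap in 7.1 applies here.

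The cost is wording only. Section 7.1 already records SUVmax for each lesion, so no scan, visit or change in sample size is needed. The downside is that one-lesion patients leave this analysis.
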